13.3 Procedures for reporting deviation(s) from the original SAP

There will be no quantitative analysis of the data collected, so no SAP will be generated.

13.4 Inclusion in analysis

All evaluable participants will be included in the analysis.

14 Analysis

14.1 Qualitative analysis

Data analysis across all phases will be purely qualitative. Audio recordings of focus groups in phase 1 and participant and HCP/ researcher interviews from the feasibility study will be transcribed verbatim. Transcripts will be subject to analysis using a framework and mapping approach followed

by a thematic analysis informed by Braun & Clarke²³ and Adu²⁴ using NVivo software as a data management tool.

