12.3 Causality

Causal relationship will be assessed for the intervention and procedures:

Intervention: VR READY mediated by DR.VR

The PI (or another delegated medically qualified doctor from the trial team) will assess each SAE to determine the causal relationship and the Chief Investigator (CI) (or another appropriately qualified member of the Trial Management Group (TMG)) can also provide this assessment where necessary:

Relationship	Description	Reasonable possibility that the SAE may have been caused by the intervention?
Unrelated	There is no evidence of any causal relationship with the intervention	No
Unlikely	There is little evidence to suggest there is a causal relationship with the intervention (e.g. the event did not occur within a reasonable time after administration of the trial medication). There is another reasonable explanation for the event (e.g. the participant's clinical condition, other concomitant treatment).	No
Possible	There is some evidence to suggest a causal relationship with the intervention (e.g. because the event occurs within a reasonable time after administration of the trial medication). However, the influence of other factors may have contributed to the event (e.g. the participant's clinical condition, other concomitant treatments).	Yes

Probable	There is evidence to suggest a causal relationship and the influence of other factors is unlikely.	Yes
Definite	There is clear evidence to suggest a causal relationship and other possible contributing factors can be ruled out.	Yes

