12.4 Expectedness

The clinical CI (or another delegated appropriately qualified individual) will assess each SAE to perform the assessment of expectedness.

SAEs which add significant information on specificity or severity of a known, already documented adverse event constitute unexpected events. For example, an event more specific or more severe than that described in the protocol is considered unexpected.

Expected adverse events from use of virtual reality headsets
Motion sickness (usually mild)
Headache (usually mild)

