12.5 Reporting Procedures

12.5.1 Participating Site Responsibilities

The PI (or delegated appropriately qualified doctor from the research team) should sign and date the SAE CRF to acknowledge that he/she has performed the seriousness and causality assessments.

A completed SAE form for all events requiring immediate reporting should be submitted via email to the VR READY study team within **24 hours** of knowledge of the event. A separate form must be used to report each event, irrespective of whether or not the events had the same date of onset.

The participant will be identified only by trial number and initials. The participant's name should not be used on any correspondence. It is also required that sites respond to and clarify any queries raised on any reported SAEs and report any additional information as soon as it becomes available (or at least within 24 hours of the information becoming available) through to the resolution of the event. Additionally, the VR READY study team may request additional information relating to any SAEs and the site should provide as much information as is available to them in order to resolve these queries.

Serious Adverse Event (SAE) email address:

[contact]

Serious adverse events should be reported from time of signature of informed consent, throughout the treatment period up to, and including completion of the follow-up timepoint.

For each **SAE** the following information will be collected:

- full details in medical terms and case description
- event duration (start and end dates, if applicable)
- action taken
- outcome
- seriousness criteria
- causality (i.e. relatedness to intervention), in the opinion of the investigator.

An SAE form is not considered as complete unless the following details are provided:

- Full participant trial number
- An Adverse Event
- A completed assessment of the seriousness, and causality as performed by the PI (or another appropriately medically qualified doctor registered on the delegation log).

If any of these details are missing, the site will be contacted and the information must be provided by the site to the VR READY study team within 24 hours.

All other AEs should be reported on the relevant CRF in the study database following the CRF procedure described in Section 16.

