14.2 Quantitative analysis

In phase 3 of the study, we will ask participants to complete the outcome measures selected through the Phase 1 activities, however, data from the completed outcome measures in phase 3 will not be analysed. Outcome measure data will be collated and summarised in a tabular format for triangulation with the interview data using a mixed methods approach²⁵ to complement their qualitative evaluation.

15 Data Management

This study will consist largely of qualitative data, with some quantitative data being collected in Phase 3, but with no plans for formal statistical analysis.

Source Data is defined as "All information in original records and certified copies of original records of clinical findings, observations or other activities in a clinical study necessary for the reconstruction and evaluation of the study. Source data are contained in source documents." There is only one set of source data at any time for any data element, as defined in site source data agreement.

Study data	Source Data				
	Participan t medical notes	CRF (paper)	CRF (electronic)	Audio file saved on S Drvie	Site file
Consent	Х				Х
Focus group data				Х	
Selected outcome measures		х	х		
Interview data				х	
Withdrawal	Х		х		х

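### The protocol names motion sickness and headache as expected VR harms and records adverse events, but its analysis sections plan no count or denominator for them

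*Protocol*

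**What the plan says.** All references are to the protocol.

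- **Named harms.** Section 12.4 has a short list headed "Expected adverse events from use of virtual reality headsets". It holds two entries, motion sickness and headache, both described as usually mild.
- **Collection.** Section 12.5.1 states: "All other AEs should be reported on the relevant CRF in the study database following the CRF procedure described in Section 16". Section 16 is in fact the section on protocol and GCP non-compliance; CRF completion is in 15.2.
- **Relatedness.** Under 12.3 the principal investigator or a delegated doctor "will assess each SAE to determine the causal relationship". No such duty is stated for non-serious events.
- **Onward reporting.** Under 12.5.2 only serious events that are both related and unexpected go to the ethics committee.
- **Analysis.** Section 14.1: "Data analysis across all phases will be purely qualitative". Section 13.3 says that no quantitative analysis will be done and that no SAP will be produced for that reason. Section 14.2 makes one provision for figures: "Outcome measure data will be collated and summarised in a tabular format for triangulation with the interview data".
- **Outcomes.** The progression criteria in 5.3 cover recruitment, retention, adherence and data completeness. Section 5.4 covers acceptability and the selected outcome measures. Neither mentions adverse events.

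**The concern.** The study collects data on the harms it expects from its intervention, yet its analysis rules give those data no place. Phase 3 is meant to inform larger studies, and the rationale in 4.1 looks for an intervention that is safe as well as acceptable. A later trial would need at least a rough frequency of motion sickness and headache for its participant information and monitoring plan.

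The gap also affects how the study's own progression criteria are read. Adherence and retention are graded red, amber or green in 5.3. If some participants stop using the headset because it makes them unwell, a low adherence figure means something different from one caused by discharge or lack of interest. Without AE counts beside it, that difference could be described in words but not sized.

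**Working it through.** The protocol gives no AE rate and no statistical sample-size calculation, so there is no stated figure to reproduce. The check is first a reading of the text, then an illustration of what a count would show.

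**Step 1. Is there any planned summary of adverse events?**

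| Place | What it provides | AEs covered? |
|---|---|---|
| 5.3 | Feasibility counts and percentages | No |
| 5.4 | Acceptability; selected outcome measures | No |
| 11.3.1 | EQ-5D, ICECAP-A, Brief Resilience Scale, Richards-Campbell, DASS-10; adherence data; interviews | None of the instruments is described as covering motion sickness or headache |
| Table 2 | Schedule of procedures | No AE row |
| 12.3, 12.4 | Causality and expectedness for each serious event | Non-serious events not covered |
| 12.5.1 | Non-serious AEs go on a CRF | Collected, no summary stated |
| 12.5.2 | Related and unexpected serious events go to the ethics committee | Mild expected events fall outside |
| 13.3 | No quantitative analysis, no SAP | No |
| 14.1 | Qualitative analysis of transcripts | No |
| 14.2 | Table of outcome measures | No |

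No section provides for counting or tabulating AEs. The usual answer, that a SAP will supply this, is closed off by 13.3.

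**Step 2. What would a count show?**

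Inputs: up to 25 patients and no more than 15 relatives expected (9.3). Relatives may join as headset users, as informants, or both (9.1), so the number of relatives using VR may be below 15. The event counts and true rates below are assumptions.

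Exact (Clopper-Pearson) 95% limits for x people with an event among n:

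- lower limit = 2.5% quantile of Beta(x, n − x + 1), or 0 if x = 0
- upper limit = 97.5% quantile of Beta(x + 1, n − x); for x = 0 this is 1 − 0.025^(1/n)

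Results:

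- 0/25: upper limit 1 − 0.025^(1/25) = 13.7%, so 0 to 13.7%
- 5/25 (20%): Beta(5, 21) and Beta(6, 20) give 6.8% to 40.7%
- 0/15 relatives: upper limit 1 − 0.025^(1/15) = 21.8%, so 0 to 21.8%

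Chance of at least one case among 25 is 1 − (1 − p)^25:

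- p = 5%: 72%
- p = 10%: 93%
- p = 20%: 99.6%

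So 25 patients would probably reveal a harm that affects one user in ten, but would estimate its frequency only roughly. All of this presumes that every event is recorded.

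**The case against.** The strongest reply is that section 14 cannot be read as a ban on everything it does not name. The primary outcome in 5.3 needs counts and percentages that section 14 never mentions, and the opening of section 15 speaks only of having no plans for formal statistical analysis. The intent may be to avoid inference, not simple tables. The study is classed as low risk (6.1), the device is CE marked (4.1), and the objectives are feasibility and acceptability.

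Much of this stands, and it limits what can be claimed. A reader might infer any of the following, and the documents do not support them:

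- *That outcome measures are the only figures the study will report.* Section 5.3 requires feasibility percentages too. None of them is a harm, however.
- *That tolerability will rest only on what participants later recall.* Section 11.3 has staff assisting for at least the first two days and checking in afterwards. Section 11.3.1 has staff interviewed during recruitment and follow-up. Section 15.1 mentions data gathered during delivery. These are real sources, but none is a planned count.
- *That mild events will never be classified by severity or relatedness.* The AE CRF is not shown. Section 12.3 requires the judgement only for serious events, but the form may still ask.
- *That the missing AE row in the section 15 source-data table shows exclusion.* That table also omits demographics and headset adherence, both of which are collected.

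It is also fair that the estimate would be weak. There is one arm, patients recovering from critical illness have other reasons for headache or nausea, and no structured symptom enquiry is scheduled, so events may be under-reported. That is a reason to label the figures descriptive, not to leave them out.

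**Conclusion.** The concern holds in a limited form. The protocol names two expected harms of VR and has non-serious AEs recorded. It then states analysis rules in 13.3, 14.1 and 14.2 that provide no count or denominator for them, with no SAP to come. This goes beyond missing detail, because a stated rule about the analysis leaves out data already being collected. It does not show that the study team would refuse to list AEs, and an unplanned listing is not prohibited.

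The consequence is modest but worth correcting. The study would forgo a descriptive estimate of roughly the precision shown above, for example 0 to 13.7% if none of 25 patients is affected. The conclusion rests on the protocol text alone. The interval figures also assume that all 25 patients are recruited and use the headset, that event recording is complete, and that the event counts are as chosen for illustration.

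**What to change.** 1. In 14.1, limit the statement about qualitative analysis to interview and focus-group data. Align 13.3, and the matching sentence in 13.1, so that descriptive counts are allowed.
2. In 14.2, add one descriptive table of AEs and SAEs. Give the number of people with at least one event and the number of events, with motion sickness and headache shown separately. Use everyone who used the headset as the denominator, put patients and relatives in separate columns, and show severity and relatedness where recorded.
3. If the AE CRF has no relatedness field, add one.
4. Correct the cross-reference in 12.5.1 so that it points to the section on CRF completion.
5. Exact 95% intervals are optional. If given, label them descriptive.

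The cost is a wording amendment, one table from data already collected, and possibly one CRF field. The downside is small: the estimates will be imprecise and may be too low, because no structured symptom enquiry is scheduled. The table should carry a note saying so.

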14.2 Quantitative analysis

In phase 3 of the study, we will ask participants to complete the outcome measures selected through the Phase 1 activities, however, data from the completed outcome measures in phase 3 will not be analysed. Outcome measure data will be collated and summarised in a tabular format for triangulation with the interview data using a mixed methods approach²⁵ to complement their qualitative evaluation.

15 Data Management

This study will consist largely of qualitative data, with some quantitative data being collected in Phase 3, but with no plans for formal statistical analysis.

Source Data is defined as "All information in original records and certified copies of original records of clinical findings, observations or other activities in a clinical study necessary for the reconstruction and evaluation of the study. Source data are contained in source documents." There is only one set of source data at any time for any data element, as defined in site source data agreement.

Study data	Source Data				
	Participan t medical notes	CRF (paper)	CRF (electronic)	Audio file saved on S Drvie	Site file
Consent	Х				Х
Focus group data				Х	
Selected outcome measures		х	х		
Interview data				х	
Withdrawal	Х		х		х

15.1 Data collection

Phase 1 Focus groups:

All focus groups will be audio recorded for verbatim transcription. During the interactive sessions, we will collate patient maps of ICU recovery and rehabilitation, as well as polling and prioritisation data from discussion on outcome measures.

Phase 3 Pilot Study:

Data from the pilot study will be largely qualitative stemming from interviews conducted with participants, family members/ loved ones and health care professionals. This data will be collected at two main

time points; one during the delivery of the intervention to gather contemporaneous reflections on the use of the intervention and one at the end of the follow-up period to gather data on the acceptability and relevance of outcome measures,. Data on the selected outcome measures will be collected prior to intervention delivery and at the end of the follow-up period as part of assessing their acceptability.

15.2 Completion of CRFs

For the phase 3 feasibility study, participants will be able to complete outcome assessments on paper or electronically. The participant's preference for CRF completion will be ascertained at the point of assessment and prior to hospital discharge (if applicable).

15.2.1 Paper CRFs

Paper CRFs will be provided to the participant by post for the follow-up assessment if requested. Completed paper CRFs will be returned to the research site using a pre-paid envelope. CRFs should be returned within four weeks of completion. Participants may be contacted by telephone if the return of paper CRFs are outstanding. This may include support for the completion of paper CRFs via telephone with a study researcher.

CRF pages and data received by the research site from participants will be checked for missing, illegible or unusual values (range checks) and consistency over time.

If missing or questionable data are identified, a researcher may contact the participant for clarification and a record of the data query will be made to inform feasibility outcomes. The case report form pages should not be altered.

Data from paper CRFs will be entered into an Excel spreadsheet by a member of the research team delegated to the study. A proportion of data entry will be checked by a second researcher on a periodic basis.

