11.3.1 Assessments

Participants will be asked to undertake assessments at baseline and after they have finished the VR intervention. The timing of the follow-up period will be informed by activities and data in Phases 1 and 2 of this study. Baseline assessments will be conducted in the hospital setting, but the follow-up assessments will be completed by participants at home either on paper to be returned to the research site, or remotely. If participants are having difficulty, or are delayed in completing the

follow-up assessments, they may be contacted by the research team to support the completion of assessments over the telephone.

Assessments will include;

- Collection of baseline demographic data to understand the diversity of the participant
 population and to contextualise any additional support requirements the participant may
 require in engaging with the intervention or completing assessments. This will be obtained
 from hospital notes for participants.
- 2) Collection of intervention adherence data, such as number of days the VR headset was used, the average length of time the VR headset was used and what aspects of the content package participants engaged with most. This data will be collected continuously by the DR.VR software during the intervention period and downloaded at the end of the intervention period.

Clinical outcome	Construct	Description	Time to	Time	
measures based on			Complete	point	
the priorities of			•	•	
ICU survivors,					
their family					
members and					
HCPs involved in					
the rehabilitation of					
ICU survivors have					
been selected,					
detailed in table 1					
People with lived					
experience have					
been involved in					
the choice of					
outcome measures,					
based on perceived					
importance and					
burden of					
assessment. Name					
EQ-5D	Quality of Life	A well validated	5 mins	Baseline	ICU
		outcome measure for		and	patients
		assessing quality of life		Follow	and
		over 5 domains across;		Up	family
		usual activities, self-			members
		care, mobility, anxiety			
		and depression and			
		pain and discomfort.			

			T	T	
		Participants are also			
		asked to rate their			
		overall quality of life			
		using a visual analogue			
		scale (0-100).			
ICECAP-A	Quality of Life	Another well validated	5 mins	Baseline	
		quality of life		and	
		instrument 5		Follow	
		questions. Wellbeing:		Up	
		feeling settled and			
		secure; love, friendship			
		and support; being			
		independent;			

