12.6 Procedure following disclosure of psychological distress

If any participant answers that they are severely or extremely anxious or depressed on the EQ5D, has a raw score of 13 or more on the DASS-10 or a score of more than 0 on DASS-10 item 12 for suicidal thoughts, this should be flagged to the clinical CI and the Critical Care clinical psychologist (contact details below).

Contact Critical Care Clinical Psychologist: Details to be added

If no one is available from the Psychology team, the Crisis team: can be contacted on:

Royal Glamorgan - [name]

Prince Charles - [name]

13 Statistical considerations

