21.1 Monitoring

The clinical study risk assessment has been used to determine the intensity and focus of central and on-site monitoring activity in the VR-READY study. Due to the low risk nature of the research and the lack of quantitative data collection, there will be no planned monitoring at site. There will be low levels of monitoring in place for qualitative data and study progress. This will be detailed in the monitoring plan.

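### A home paper form reporting suicidal thoughts may come back four weeks after completion, and no time is set for scoring or flagging any form under 12.6

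*Protocol*

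**What the plan says.** Protocol section 12.6 sets three triggers: anxiety or depression at the severe or extreme level on the EQ-5D, a DASS-10 raw score of 13 or above, or "a score of more than 0 on DASS-10 item 12 for suicidal thoughts". If any is met, "this should be flagged to the clinical CI and the Critical Care clinical psychologist", with the Crisis team as fallback when nobody in Psychology is available. The section names no one to do the scoring and gives no time limit.

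The instrument table in 11.3.1 schedules both questionnaires at baseline and follow-up, for patients and family members, and describes the DASS-10 as a 10-item form. On follow-up, 11.3.1 says that "the follow-up assessments will be completed by participants at home either on paper to be returned to the research site, or remotely". Section 11.3 lets the participant choose paper, electronic or telephone completion, and has those still in hospital assessed there.

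For paper, section 15.2.1 says "CRFs should be returned within four weeks of completion". Forms received "will be checked for missing, illegible or unusual values (range checks) and consistency over time", and the data are then entered in a spreadsheet. A telephone call about an outstanding form is allowed but not required. Section 15.2.2 describes an emailed link for electronic completion and does not say when the answers are read, or by whom.

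**The concern.** A safety trigger works only if someone reads the answer soon after it is given. Here the trigger depends on two questionnaires, and the data-handling rules for one permitted route let those questionnaires stay unseen for four weeks. This is more than a missing detail: a stated return window works against a stated safety procedure. It also cannot be left to a statistical analysis plan, because it concerns participant safety and because section 13.3 says no such plan will be written.

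At stake is whether a distressed patient or relative reaches the clinical CI and the psychologist in time for it to help. The paper route is used mainly after discharge, when research staff are no longer at the bedside. A second weakness is that the most serious trigger points to an item number that the described form does not have.

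**Working it through.** The plan gives no figure to reproduce. The check sets the sections side by side and works out the delay that they permit.

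**People and forms.** Section 9.3 gives up to 25 patients and expects no more than 15 relatives, so at most 25 + 15 = 40 people. Table 2 marks the outcome measures at one follow-up (week 2), giving at most 40 × 1 = 40 follow-up sets. Section 11.3 speaks of assessments at 2 and 4 weeks, giving at most 40 × 2 = 80. These are ceilings. Section 9.1 allows some relatives to take part only as sources of information.

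**Delay by route, from answer to flag.**

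| Route | Answer given to answer seen by staff | Answer seen to flag raised |
|---|---|---|
| Baseline, read out by staff (11.3) | At once | Not stated |
| Follow-up by telephone (11.3) | At once | Not stated |
| Electronic at home (15.2.2) | Review time not stated | Not stated |
| Paper at home (15.2.1) | Up to 4 weeks = 28 days | Not stated |

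**Calendar for paper**, if the form is completed on its due date:
- week-2 form: 2 + 4 = week 6
- week-4 form, if that follow-up applies: 4 + 4 = week 8

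The unstated time for scoring and flagging comes on top.

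**Does anything else close the gap?**
- The receipt checks in 15.2.1 look for missing, illegible, out-of-range or inconsistent entries. A legitimate DASS-10 total of 13 passes a range check. The checks are not a comparison with the 12.6 thresholds.
- The telephone call in 15.2.1 is optional and concerns outstanding forms. A form still inside its four weeks need not count as outstanding. The four weeks also run from completion, a date that the site does not know until a home form arrives.

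**The item number.** Section 12.6 cites item 12, while 11.3.1 describes 10 items, so the reference cannot be followed as written. The total score is no substitute: the item trigger fires at any score above 0 and the total trigger only at 13, so a person can report suicidal thoughts without reaching the total.

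**The case against.** The strongest reply is that 28 days is an outer limit, not an expected delay. Participants get a pre-paid envelope, and most people post a form soon after completing it. Every returned form is handled by a delegated researcher, and the Crisis team fallback in 12.6 shows that prompt action is intended once an answer is seen. Patients still in hospital at week 2 are assessed there. A turnaround time could sit in a working instruction. All of this narrows the problem and keeps it minor. It does not remove the written four-week permission, and a working instruction on turnaround would not shorten that window.

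A reader might also infer four stronger points, which the documents do not support.
- *That the monitoring decision is unsound.* Section 21.1 says "Due to the low risk nature of the research and the lack of quantitative data collection, there will be no planned monitoring at site", while section 15 describes the study as one "with some quantitative data being collected in Phase 3, but with no plans for formal statistical analysis". The wording in 21.1 is loose, but correcting it changes nothing that the trial does. Site monitoring is quality assurance, not the route by which a distress score is acted on.
- *That leaving outcome data unanalysed blocks the trigger.* Section 14.2 says "data from the completed outcome measures in phase 3 will not be analysed", but this does not stop anyone acting on a single form under 12.6.
- *That 28 days should be set against the 24-hour limit for serious adverse events.* The clocks differ. The 24 hours run from knowledge of the event and the 28 days from completion of the form. The like-for-like interval, receipt to flag, is simply not stated.
- *That a delayed flag is likely.* The documents give neither the share of participants choosing paper nor the share meeting a trigger, so any probability would rest on assumptions alone.

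**Conclusion.** The point holds as a minor safety defect. Under the written rules, a home paper form that meets a 12.6 trigger may reach staff up to 28 days after completion, and no route has a stated time for scoring or flagging. In calendar terms, a week-2 form may arrive as late as about week 6. The week-8 figure depends on the 4-week follow-up in 11.3 carrying the questionnaires, which Table 2 does not show. At most 40 people are exposed to the follow-up trigger, and the long delay concerns only those who use paper at home. If nobody does, it does not arise, though the missing scoring time and the wrong item number remain. The 28 days come straight from 15.2.1 and need no assumption; the week figures assume completion on the due date.

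**What to change.** (a) In 12.6, require a delegated researcher to score the DASS-10 and EQ-5D against the triggers on the day they are completed with staff or received, whether on paper or electronically. Any flag goes to the clinical CI and psychologist, or to the Crisis team if Psychology is unavailable, the same working day. Identify the suicidal-thoughts item by its wording instead of a number.

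(b) In 15.2.1, replace the four-week window for these two forms with prompt return, for example posting within 2 days of completion. Require a telephone call if they have not arrived within about one week of the due date. The due date is the better clock because the site knows it. The other paper forms can keep four weeks.

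Telephone completion should be offered on that call but not made compulsory. Compulsion would override the choice of method in 11.3 and 15.2. It would also stop the paper versions of these two measures being tested, although acceptability of the outcome measures is a Phase 3 secondary objective (5.2).

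The cost is two short wording changes and a few hours of staff time for scoring and reminder calls. A call that ends in completing both forms takes about 7 + 5 = 12 minutes by the times in the 11.3.1 table, so ten such calls take 10 × 12 = 120 minutes, or 2 hours.
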